11.1.5 Significant Adverse Events

Other significant AEs are defined as marked hematological and other laboratory abnormalities (other than those meeting the definition of serious) and any events that led to an intervention, including withdrawal of test drug, dose reduction, or significant additional concomitant therapy.

11.1.6 Treatment-Emergent Adverse Events

An AE is defined as treatment emergent if the first onset or worsening is after the first application of IP (trifarotene or vehicle) and not more than 14 days after the last application of IP.

11.2. Event Assessment and Follow-up of Adverse Events

The occurrence of an AE or SAE may come to the attention of study personnel during study visits and interviews of a study participant presenting for medical care or upon review by a study monitor.

All reported AEs, including local and systemic AEs not meeting the criteria for SAEs, will be captured on the appropriate eCRF. Information to be collected includes event description, time of onset, clinician's assessment of severity, relationship to study product (assessed only by those with the training and authority to make a diagnosis), and time of resolution/stabilization of the event. All reported AEs occurring while on study must be documented appropriately regardless of relationship. All reported AEs will be followed to adequate resolution.

Any medical condition that is present at the time that the participant is screened will be considered as baseline and not reported as an AE. However, if the study participant's condition deteriorates at any time during the study, it will be recorded as an AE.

Changes in the severity of a reported AE will be documented to allow an assessment of the duration of the event at each level of severity to be performed. AEs characterized as intermittent require documentation of onset and duration of each episode.

Study clinic personnel will record all reportable events with start dates occurring any time after informed consent is obtained until 14 (for nonserious AEs) or 30 days (for SAEs) after the last day of study participation. At each study visit, the investigator will inquire about the occurrence of AE/SAEs since the last visit. Events will be followed for outcome information until resolution or stabilization.

11.2.1 Assessment

The investigator is responsible for the detection and documentation of events meeting the criteria and definition of an AE or SAE described previously. At each visit, the subject will be allowed time to spontaneously report any issues since the last visit or evaluation. The investigator will then monitor and/or ask about or evaluate AEs using nonleading questions, such as

- “How are you feeling?”
- “Have you experienced any issues since your last visit?”
- “Have you taken any new medications since your last visit?”

Any clinically relevant observations made during the visit will also be considered AEs. In addition, although local tolerability will be assessed on a 0-3 scale, all application site reactions should be recorded as AEs.

11.2.2 Evaluation

11.2.2.1 Severity of Adverse Events

The clinical severity of an AE will be classified as follows:

Mild	Usually transient and may require only minimal treatment or therapeutic intervention. The event does not generally interfere with usual activities of daily living.
Moderate	Usually alleviated with additional specific therapeutic intervention. The event interferes with usual activities of daily living, causing discomfort but poses no significant or permanent risk of harm to the subject.
Severe	Interrupts usual activities of daily living, or significantly affects clinical status, or may require intensive therapeutic intervention.

It is important to distinguish between severe AEs and SAEs. Severity is a classification of intensity whereas an SAE is an AE that meets serious criteria, as described in Section [11.1.4](#).

11.2.2.2 Seriousness

The investigator is to evaluate whether the AE meets serious criteria, as described in Section [11.1.4](#).

11.2.2.3 Action(s) Taken

All AEs will be treated/managed according to standard practice. The following actions may be taken with regard to the IP. Section [9.4](#) describes dose adjustment and stopping rules for individual subjects.

Action(s) taken may consist of the following:

Dose not changed	An indication that a medication schedule was maintained.
Dose reduced	An indication that a medication schedule was modified by subtraction, either by changing the frequency, strength, or amount.
Drug interrupted	An indication that a medication schedule was modified by temporarily terminating a prescribed regimen of medication.
Drug withdrawn	An indication that a medication schedule was modified through termination of a prescribed regimen of medication.
Not applicable	Determination of a value is not relevant in the current context.
Unknown	Not known, not observed, not recorded, or refused.

11.2.2.4 Outcome at the Time of Last Observation

The outcome of an AE at the time of last observation will be classified as follows:

- Recovered/resolved
- Recovered/resolved with sequelae
- Recovering/resolving
- Not recovered/not resolved
- Fatal*
- Unknown

*Only select fatal as an outcome when the AE results in death. If more than one AE is judged to be possibly related to the subject's death, the outcome of death should be indicated for each such AE. Although "fatal" is usually an event outcome, events such as sudden death or unexplained death should be reported as SAEs.

11.2.2.5 Adverse Event Relationship to Investigational Product

The investigator must make an assessment of each AE's relationship to the IP. The categories for classifying the investigator's opinion of the relationship are as follows:

Not related	An AE with sufficient evidence to accept that there is no causal relationship to IP administration (e.g., no temporal relationship to drug administration, because the drug was administered after onset of event; investigation shows that the drug was not administered; another cause was proven.)
Unlikely related	An AE, including laboratory test abnormality, with a temporal relationship to IP administration that makes a causal relationship improbable, and in which other drugs, events, or underlying disease provide plausible explanations.
Possibly related	An AE with a reasonable time sequence to administration of the IP, but that could also be explained by concurrent disease or other drugs or events. Information on drug withdrawal may be lacking or unclear.
Related	An AE occurring in a causal plausible time relationship to IP administration that cannot be attributed to a concurrent disease or other drugs, chemicals, or events. The AE relationship to the IP must be assessed separately by the investigator and Mayne Pharma LLC.

11.2.3 Documentation

Any AE that occurs during the Screening Period will be captured as on the AE page of the eCRF (not medical history). All AEs that occur within the period of observation for the study must be documented in the eCRF with the following information, where appropriate. (The period of observation for the study is described in Section 11.2.)

- AE name or term
- When the AE first occurred (start date and time)
- When the AE stopped (stop date and time or an indication of “ongoing”)
- Severity of the AE
- Seriousness (hospitalization, death, etc.)
- Actions taken
- Outcome
- Investigator opinion regarding the AE relationship to the IP(s)

11.2.4 Treatment of Adverse Events

Adverse events that occur during the study will be treated, if necessary, by established standards of care. If such treatment constitutes a deviation from the protocol, the subject may be withdrawn for treatment but continue to be followed for efficacy and safety in the study. The decision about whether the subject may continue in the study will be made by the sponsor after consultation with the investigator and/or medical monitor.

If AEs occur in a subject that are not tolerable, the investigator must decide whether to stop the subject’s involvement in the study and/or treat the subject. Special procedures may be recommended for the specific IP, such as the collection of a serum sample for determining blood concentrations of IP, specific tapering procedures, or treatment regimens, as appropriate.

It is not necessary to unblind a subject’s treatment assignment in most circumstances, even if an SAE has occurred. If unblinding is necessary, see Section 9.6 for a description of the unblinding procedures.

11.2.5 Follow-up

Any AE will be followed (up to a maximum of 14 days after the last dose of IP) to a satisfactory resolution, until it becomes stable, or until it can be explained by another known cause(s) (i.e., concurrent condition or medication) and clinical judgment indicates that further evaluation is not warranted. All findings relevant to the final outcome of an AE must be reported in the subject’s medical record and recorded on the eCRF page.

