10.2.2.7 Visit 6 (90 ±7 days) or Early Termination

The following procedures will be performed on Day 90 in the study clinic:

1. Record responses to DLQI and EQ-5D Quality of Life Questionnaires (see Sections 10.3.1.6 and 10.3.1.7 for which version of questionnaire to use).
2. Perform a physical examination.
3. Record vital signs (blood pressure and pulse).
4. Record concomitant medications and concomitant therapies.
5. Record IGA.
6. Record VIIS.
7. Record roughness assessment.
8. Record palm/sole assessment.
9. Record palm/sole assessment of fissuring.
10. Record ectropion score.
11. At sites where the optional photographic substudy is conducted, take photographs of subjects who have provided informed consent for the substudy.
12. Assess local tolerance.
13. Record AEs and review diary.
14. Perform a 12-lead ECG.
15. Perform a urine pregnancy test for WOCBP.
16. Collect blood and urine for routine laboratory tests (subject must be fasting at least 8 hours).
17. Collect a PK blood sample (all subjects).
18. Collect returned study drug tubes; confirm study drug compliance by weighing returned tube contents and reviewing diaries.

For subjects who successfully complete (i.e., have reliable visit attendance and compliance with IP application, in the investigator's opinion) the initial 12 weeks of double-blind treatment and choose to continue into the OLE, this visit will be the first visit of that portion of the study. All efficacy assessments, safety/tolerability assessments, including clinical laboratory testing, PK from Day 90/Week 12 will be carried over to the OLE and will not be repeated. Subjects will have up to 7 days to decide to enter the OLE; if the subject chooses to continue into OLE, the following additional procedures will be done:

1. Have the subject sign OLE-specific informed consent.
2. Measure subject's weight.
3. Instruct subject on study drug application, and advise subjects regarding permitted emollient(s) and/or sunscreen for use on nontreatment days; use of emollient(s) on study drug treatment days within 4 hours before or after study drug application is prohibited.

Remind subjects that at least 24 hours must have elapsed since IP application before the PK draws at the Week 16 and Week 24 Visits, and not to apply IP on visit days until after the visits.

4. Weigh new study drug tubes and dispense enough additional study drug until next visit (only for subjects who choose to continue into the OLE).
5. Dispense study diary.

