10.2.3 Follow-up Telephone Call (± 14 days after Day 90) – Only Subjects Who Do Not Continue into Open-label Extension

Clinic staff will telephone subjects who choose not to continue into the Open-label Extension within 14 days after Day 90 to assess any ongoing AEs.

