10.2.4.7 Follow-up Evaluation – Open-Label Extension (Week 26/Visit 11)

At 14 days after the last administration of the IP, the following procedures will be performed:

1. Perform a physical examination.
2. Record vital signs (blood pressure and pulse).
3. Record any concomitant medications/therapies.
4. Record IGA.
5. Record VIIS.
6. Assess roughness.
7. Record palm/sole assessment.
8. Record palm/sole assessment of fissuring.
9. Record ectropion score.
10. Assess and record AEs occurring since the last evaluation and review diary.
11. Perform a urine pregnancy test for WOCBP.

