10.3.4.1.3 Evaluation of Clinical Laboratory Values

The normal ranges of values for the clinical laboratory assessments in this study will be provided by the responsible laboratory and submitted to Mayne Pharma LLC prior to beginning the study. They will be regarded as the reference ranges on which decisions will be made.

If a laboratory value is out of the reference range, it is not necessarily clinically significant. The investigator must evaluate the out-of-range values and record his or her assessment of the clinical significance in the appropriate eCRF.

All clinical laboratory values that in the investigator's opinion show clinically significant or pathological changes during or after termination of treatment must be reported as AEs and followed, as described in Section 11.2.5.

All measurements described in this section are recognized standard methods.

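### Section 11.2.5 ends follow-up of any AE, SAEs included, 14 days after the last dose, while Section 11.2 follows events to resolution or stabilization with no time limit

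*Protocol*

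**What the plan says.** Protocol Section 11.2 (Amendment 1) gives the follow-up duty twice, each time without a day limit: "All reported AEs will be followed to adequate resolution" and "Events will be followed for outcome information until resolution or stabilization". The same section sets the period in which new events are recorded, by start date: from consent "until 14 (for nonserious AEs) or 30 days (for SAEs) after the last day of study participation".

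Section 11.2.5, which sits under 11.2, gives the duty again with a limit: "Any AE will be followed (up to a maximum of 14 days after the last dose of IP) to a satisfactory resolution". The sentence goes on to allow an earlier end if the event is stable or otherwise explained. It has no exception for SAEs.

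Section 10.3.4.1.3 refers clinically significant laboratory changes to the capped rule: they "must be reported as AEs and followed, as described in Section 11.2.5". Section 8.3 refers AEs that cause withdrawal to Section 11.2, the uncapped one.

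The original protocol contains the same pair of statements in its Sections 11.2 and 11.2.5.

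**The concern.** The two sections give sites opposite instructions about the same events. For an event still open on day 15 after the last dose, 11.2 says to continue and 11.2.5 says the duty has ended. The protocol does not rank the two.

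If a site follows 11.2.5, what is at risk is the later course of SAEs and clinically significant laboratory changes that are unresolved at the cap. This bites mainly once no further visit is scheduled. It matters here because Section 9.4.1 makes clinically significant liver and lipid changes a mandatory reason to stop treatment, and because Cohort B includes adolescents.

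**Working it through.** No sample size, power or alpha figure is involved. The check is a comparison of texts plus day counting.

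**1. Does the cap reach SAEs?** Section 11.2.2.1 describes an SAE as an AE that meets the serious criteria. The rule in 11.2.5 covers any AE. It therefore includes SAEs.

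**2. Can the two rules be read together?** The other end conditions in 11.2.5 (resolved, stable, explained by another cause) do not remove the limit, because the parenthesis applies to the whole sentence. Elsewhere the protocol writes a separate rule where it wants longer follow-up: QT prolongation to full resolution (Section 10.3.4.2.2) and pregnancy to delivery or termination (Section 11.3.2). It has no such rule for SAEs. The contradiction stands within one version.

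**3. How does the cap sit with the SAE recording window?** Count days from the last dose, with the cap at day 14. The last day of study participation is not defined, so both readings are shown.

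- Participation ends at the last dose: SAEs are recordable to day 30. Onsets after the cap fall on days 15 to 30, and 30 − 14 = 16 days.
- Participation ends at the follow-up contact 14 days after the last dose (Section 10.1.1): SAEs are recordable to day 14 + 30 = 44. Onsets after the cap fall on days 15 to 44, and 44 − 14 = 30 days.
- On the second reading nonserious AEs are recordable to day 14 + 14 = 28, so 28 − 14 = 14 days of recordable onsets fall after the cap. On the first reading the figure is 14 − 14 = 0.

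An SAE that starts in these 16 or 30 days must be recorded, although its follow-up limit has already passed.

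**4. Laboratory changes first seen at the last scheduled test.** That test is at Day 90 without the extension ("Collect blood and urine for routine laboratory tests (subject must be fasting at least 8 hours") and at Day 180 with it (Section 10.2.4.6). Both visits include a PK sample and so must be at least 24 hours after the last application (Section 9.2). On nominal visit days:

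- No extension: last dose at latest 90 − 1 = Day 89; cap 89 + 14 = Day 103; remaining 103 − 90 = 13 days.
- Extension: last dose at latest 180 − 1 = Day 179; cap 179 + 14 = Day 193; remaining 193 − 180 = 13 days.

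A laboratory change first seen there has at most 13 days of follow-up under the capped rule. The remaining scheduled contact is a telephone call "within 14 days after Day 90 to assess any ongoing AEs" (Section 10.2.3) or Visit 11, where the safety item reads "Assess and record AEs occurring since the last evaluation and review diary".

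**The case against.** Several points on the other side stand and set the limits of the claim.

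- **The 30-day window.** A reader might infer that it is a second contradiction of the cap. It is not. It governs which onsets are recorded, and 11.2.5 governs how long events are followed. The day counts in step 3 show that the cap does not work for late SAEs and nothing more.
- **Loss of outcomes.** A reader might infer that SAE outcomes would simply be lost. The documents do not support that. The second sentence of 11.2.5 still requires findings relevant to the final outcome to be recorded, with no day limit. Section 11.2.2.4 offers unresolved outcome categories, and Section 11.2.3 allows an event to be entered as ongoing. Section 11.2.6.1 asks for further SAE information on a follow-up form and lets pharmacovigilance request more. Section 11.2.6.2 requires suspected serious ADRs to be reported whenever they arise. These rules govern recording and reporting. They soften the cap but do not lift it.
- **No scheduled laboratory retest.** A reader might take this as a defect. Retesting an abnormal value is normally driven by the event, and nothing forbids it within the 13 days. The point is only that such changes are referred to the capped rule.
- **Subjects who stop treatment early.** Those who stay in the study keep AE review at visits and the Day 90 tests (Section 8.4 and Table 2-1), and Section 11.2.4 provides for continued safety follow-up. The documents do not require a separate exception for AEs that lead to discontinuation of treatment.
- **Version.** The file opens with the closing sections of another protocol version whose Section 11 is not shown. If that version is the operative one, the conflict may already have been removed, and this cannot be settled from the file.

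**Conclusion.** The contradiction is real in both versions whose Section 11 is shown. Section 11.2 sets uncapped follow-up, Section 11.2.5 caps the same duty at 14 days after the last dose with no SAE exception, and nothing says which prevails. The two sections also count from different dates.

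The size is minor. Only events unresolved at the cap, or SAEs starting after it, are affected. TEAEs are classified by onset or worsening, so their incidence does not change, and no efficacy analysis is involved. The 16-day and 30-day figures rest on the two assumed ends of participation. The 13-day figure rests on nominal visit days and the latest permitted last dose.

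**What to change.** First check Section 11 of the version whose closing sections open the file. If the wording persists, amend 11.2.5 as follows:

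- Delete the 14-day cap, or restrict it to nonserious AEs.
- State that SAEs, including those starting in the 30-day window, and clinically significant laboratory changes are followed until resolution, stabilization or loss to follow-up.
- Align the two follow-up sentences in 11.2 with this rule, and use one defined anchor date in both sections. If the cap is kept for nonserious AEs, the common anchor is also what closes the possible 14-day gap for them.

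The cost is a wording change through a protocol amendment with IRB/IEC approval, plus a few extra follow-up contacts or retests. Their number cannot be estimated from the protocol.

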11.2.6 Reporting

11.2.6.1 Serious Adverse Events

The investigator or designee must report all SAEs promptly to Premier Research within 24 hours of first becoming aware of the event by e.g., completing, signing and dating the Serious Adverse Event Report Form, verifying the accuracy of the information recorded in the form with the source documents and eCRF, and sending the SAE form to the Premier Research by one of the following methods:

Email: [contact]

Email: [contact]

[contact]

[contact]

This written report should be submitted on the SAE form provided for this purpose. At the time of first notification, the investigator or designee should provide the following information, if available:

- Protocol number
- Reporter (study site and investigator)
- Suspect IP
- Subject's study number
- Subject's year of birth
- Subject's gender
- Date of first dose of IP(s)
- Date of last dose of IP(s), if applicable
- Adverse event term
- Date of occurrence of the event
- A brief description of the event, outcome to date, and any actions taken
- The seriousness criteria(on) that were met
- Concomitant medication at onset of the event
- Relevant medical history information
- Relevant laboratory test findings
- Investigator's opinion of the relationship to IP(s) ("Is there a reasonable possibility that the IP caused the SAE? Yes or No?")
- Whether and when the investigator was unblinded as to the subject's treatment assignment

Any missing or additional relevant follow-up information concerning the SAE should be sent to the sponsor/sponsor representative via the same contact details above as soon as possible on a follow-up SAE Report Form, together with the following minimal information (initial report, adverse event, date of occurrence, subject identification (ID), study ID, IP, and site number); this will allow the follow-up information to be linked to the initial SAE report.

Specific information may be requested by the Premier Research Pharmacovigilance Department using a follow-up request form or via email communication.

The investigator is required to comply with applicable regulations (including local laws and guidances) regarding the notification of his or her health authorities, institutional review board (IRB)/independent ethics committee (IEC), principal and coordinating investigators, study investigators, and institutions. Each investigator is obligated to learn about the reporting requirements for investigators in his/her country. The study monitor may be able to assist with this.

11.2.6.2 Adverse Drug Reactions

All ADRs should be reported by the investigator in the eCRF.

Suspected serious ADRs must be reported to the sponsor immediately, regardless of the time elapsed since the end of the observation period.

11.2.6.3 Nonserious Adverse Events

Nonserious AEs will be recorded in the eCRF and reported by Premier Research to Mayne Pharma LLC in aggregate monthly status reports.

